- Any concurrent ocular or intraocular condition (e.g., cataract or diabetic retinopathy) that, in the opinion of the investigator, would require medical or surgical intervention during the study period to prevent or treat vision loss that might result from that condition
- Active inflammatory (e.g., uveitis or vitritis) or infectious (e.g., conjunctivitis, keratitis, scleritis, or endophthalmitis) conditions in either eye or history of idiopathic or autoimmune-associated uveitis in either eye
- Requirement for daily supplemental oxygen
- Symptomatic active lung disease, including pneumonitis
- History of or active inflammatory bowel disease (e.g., Crohn's disease or ulcerative colitis)
 - Patients currently receiving immunosuppressants for inflammatory bowel disease (e.g., sulfasalazines) are considered to have active disease and are *thus* ineligible.
- Any active bowel inflammation (including diverticulitis)
- Symptomatic hypercalcemia requiring continued use of bisphosphonate or denosumab therapy
 - Bisphosphonate and denosumab therapy for bone metastases or osteopenia/osteoporosis is allowed.
- Clinically significant and active liver disease, including severe liver impairment (Child-Pugh Class B/C), viral or other hepatitis, current alcohol abuse, or cirrhosis
- Known HIV infection
 - Sites should include an HIV test during screening, as allowed per local regulations.
- Current severe, uncontrolled systemic disease (e.g., clinically significant cardiovascular, pulmonary, metabolic, or infectious disease) or any other diseases, active or uncontrolled pulmonary dysfunction, metabolic dysfunction, physical examination finding, or clinical laboratory finding giving reasonable suspicion of a disease or condition that contraindicates the use of an investigational drug, that may affect the interpretation of the results, or that renders the patient at high risk from treatment complications
- Chemotherapy, radiotherapy, or any other anti-cancer therapy within 2 weeks before randomization

- Investigational drug(s) within 4 weeks before randomization
- Prior radiotherapy to $\geq 25\%$ of bone marrow, or hematopoietic stem cell or bone marrow transplantation
- Unresolved toxicity from prior therapy, except for hot flashes, alopecia, and Grade ≤ 2 peripheral neuropathy

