Other local radiotherapy is not permitted with the following exception. It is understood that there may be circumstances requiring local radiotherapy in which the investigator does not believe that the symptoms are a result of disease progression (e.g., impending fracture) and the radiation field does not encompass a target/non-target lesion. In such cases, the patient should have a tumor assessment of the lesion(s) before they receive radiotherapy. If a patient received radiation therapy and a target or non-target lesion was included in the field of radiation, the lesion(s) will become unevaluable for tumor response.

Further reasons for avoiding local radiotherapy include the difficulty in distinguishing new symptomatic pain or worsening of lytic bone lesions from disease progression. Time-to-Deterioration in Pain is a secondary endpoint of this study and Time-to-First-Skeletal-related-Event is an exploratory endpoint; palliative radiotherapy may alter these results. As such, palliative radiotherapy to bone in the absence of disease progression may be allowed after consultation with the Medical Monitor, however, such patients will be censored from the aforementioned

secondary and exploratory endpoints. Few clinical data are available about potential toxicities of radiation and treatment with inavolisib. Study treatment should be held ~24 hours prior to palliative radiotherapy and until any effects or sequelae have resolved to Grade \leq 1. Patients should not miss more than one cycle of study treatment due to radiation treatment and must meet eligibility requirements to continue *in the* study treatment (Section 4.1.1). Previous clinical experience also suggests that new bone pain is frequently a symptom of disease progression. Bone pain secondary to fulvestrant treatment may be treated with pain medications, nonsteroidal anti-inflammatory drugs (NSAIDs), or corticosteroids.

- Primary prophylactic use of hematopoietic growth factors (e.g., erythropoietins, granulocyte colony-stimulating factor [G-CSF], and *granulocyte-macrophage colony-stimulating factor* is not permitted, however, they may be used to treat treatment-emergent neutropenia or anemia as indicated by the current ASCO guidelines or as secondary prophylaxis if dose reduction or delay is not considered a reasonable alternative.

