5.3.1 Adverse Event Reporting Period

Investigators will seek information on adverse events at each patient contact. All adverse events, whether reported by the patient or noted by study personnel, will be recorded in the patient's medical record and on the Adverse Event eCRF.

After informed consent has been obtained but prior to initiation of study drug, only serious adverse events caused by a protocol-mandated intervention (e.g., invasive procedures such as biopsies, discontinuation of medications) should be reported (see Section 5.4.2 for instructions for reporting serious adverse events).

After initiation of study drug, all adverse events will be reported until 30 days after the final dose of any study drug (i.e., 30 days after the final study treatment with inavolisib/placebo or palbociclib or fulvestrant, whichever is last), or until initiation of another anti-cancer therapy, whichever occurs first. After this period, the investigator should report any serious adverse events that are believed to be related to prior study drug treatment (see Section 5.6).

Instructions for reporting adverse events that occur after the adverse event reporting period are provided in Section 5.6.

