5.3.5.9 Lack of Efficacy or Worsening of Breast Cancer

Events that are clearly consistent with the expected pattern of progression of the underlying disease should not be recorded as adverse events. These data will be captured as efficacy assessment data only. In most cases, the expected pattern of progression will be based on RECIST v1.1. In rare cases, the determination of clinical progression will be based on symptomatic deterioration. However, every effort should be made to document progression through use of objective criteria. If there is any uncertainty as to whether an event is due to disease progression, it should be reported as an adverse event. Cases of clinical/symptomatic progression will not be considered as objective disease progression per RECIST v1.1, and should be reported only as a

reason for End of Treatment, when appropriate. The Overall Tumor Assessment at such a timepoint should be reported strictly per RECIST v1.1.

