6.4.3 Exploratory Efficacy Endpoints

6.4.3.1 Exploratory Clinical Outcomes

- Time to end of next-line treatment (proxy for time to second objective disease progression [PFS2]), defined as the time from randomization to end or discontinuation of next-line treatment, or death from any cause (whichever occurs first). Data for patients without the occurrence of second objective disease progression or death and patients who have not started next-line treatment will be censored at the last date they were known to be alive. Data from patients without post-baseline information will be censored at the date of randomization. Analysis methodology is as outlined for the primary endpoint, PFS.
- Time to first SRE, defined as the time from randomization to the first occurrence of an SRE. An SRE is a pathologic fracture, radiation therapy to bone, cancer-related surgery to bone, or spinal cord compression. Data from patients without the occurrence of an SRE will be censored at the last valid visit. Data from patients without post-baseline information will be censored at the date of randomization. Analysis methodology is as outlined for the primary endpoint, PFS.

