- ^e POST-TREATMENT TUMOR ASSESSMENT FOLLOW-UP WITH PRO COLLECTION - Patients who discontinue active study treatment for reasons other than progression of disease or death will continue to have tumor assessments performed every 8 weeks (± 7 days) for the first 2 years from randomization and every 12 weeks (± 7 days) thereafter, and complete PRO assessments at those timepoints until documented disease progression or the initiation of another anti-cancer therapy, whichever occurs first.
- ^f SURVIVAL FOLLOW-UP PERIOD - After study treatment discontinuation and post-treatment follow-up, all patients will be followed for survival and all subsequent anti-cancer therapies. These data will be collected approximately every 3 months until death, loss to follow-up, withdrawal of consent, or study termination by the Sponsor, whichever occurs first.
- ^g INFORMED CONSENT - Informed consent must be documented before any study-specific screening procedure is performed and may be obtained more than 28 days before initiation of study treatment.
- ^h VITAL SIGNS - Includes height, weight, respiratory rate, pulse rate, blood oxygenation (pulse oximetry), and systolic and diastolic blood pressure while the patient is in a seated position, and temperature.

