Appendix 1: Schedule of Activities

- ji **POST-TREATMENT ANTI-CANCER THERAPY** - After study treatment discontinuation, all patients will be followed for subsequent anti-cancer therapies. These data will be collected via telephone calls and/or clinic visits during the post-treatment follow-up and survival follow-up, approximately every 3 months until death, loss to follow-up, withdrawal of consent, or study termination by the Sponsor, whichever occurs first.
- kk **SURVIVAL** - After study treatment discontinuation and post-treatment follow-up, all patients will be followed for survival. These data will be collected via telephone calls and/or clinic visits approximately every 3 months until death, loss to follow-up, withdrawal of consent, or study termination by the Sponsor, whichever occurs first.

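### Time to first SRE has no documented collection route and an undefined censoring date, so time in which an SRE could not be seen may count as event-free

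*Protocol*

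**What the plan says.** Time to first SRE is an exploratory efficacy endpoint (Protocol 2.1.3 and 6.4.3.1, SAP 4.4). It is measured from randomization, and neither document ends it at progression. On the event, Protocol 6.4.3.1 says: "An SRE is a pathologic fracture, radiation therapy to bone, cancer-related surgery to bone, or spinal cord compression". On censoring: "Data from patients without the occurrence of an SRE will be censored at the last valid visit". SAP 4.4 repeats both statements, and neither document defines a valid visit.

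On collection:
- The Appendix 1 schedule has no SRE row at any visit.
- Protocol 5.3.1: "all adverse events will be reported until 30 days after the final dose of any study drug", or until another anti-cancer therapy starts if that is sooner. After that, Protocol 5.6 asks only for deaths and for serious events believed related to study treatment.
- Protocol 5.3.5.9: "Events that are clearly consistent with the expected pattern of progression of the underlying disease should not be recorded as adverse events".
- In survival follow-up (Appendix 1, footnote f), "all patients will be followed for survival and all subsequent anti-cancer therapies". Of the therapy data, footnote jj says: "These data will be collected via telephone calls and/or clinic visits during the post-treatment follow-up and survival follow-up". Footnote hh adds one patient-reported outcome assessment at about three months.

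Protocol 4.4.3 has a second rule. Of patients given palliative bone radiotherapy without progression, it says that "such patients will be censored from the aforementioned" endpoints. Those are time to deterioration in pain and time to first SRE.

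**The concern.** A patient should be censored no later than the last date on which the event could have been seen. The plan's other time-to-event endpoints follow this: PFS and duration of response stop at the last tumor assessment, the deterioration endpoints at the last non-missing questionnaire, and OS at the last date known alive. SRE is the exception.

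After study treatment the documented routes to an SRE mostly close. Bone radiotherapy may still surface as a subsequent therapy, since the protocol elsewhere counts radiotherapy as anti-cancer therapy ("Chemotherapy, radiotherapy, or any other anti-cancer therapy within 2 weeks before randomization", Protocol 4.1.2). Nothing says that the irradiated site is recorded, however, and no route is described for a later fracture, bone surgery or cord compression. The composite therefore changes content at about progression.

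What follows depends on how *last valid visit* is read. If it includes survival contacts, patients add event-free time in which most SREs could not be recorded. That time starts earlier in the arm that progresses earlier, which under the plan is control, so equal SRE risk could look worse on inavolisib. If it means the last visit with SRE ascertainment, the comparison is fair but later SREs are lost. Two programmers could choose different dates, and both would be following the text.

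Separately, bone radiotherapy without progression is a censoring reason in Protocol 4.4.3 and an event in 6.4.3.1.

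**Working it through.** **Plan's own figure.** There is none for SRE, so the PFS inputs were checked. Schoenfeld events for HR 0.65, two-sided 0.05 and 85% power: 4 × (1.960 + 1.036)² / (ln 0.65)² = 35.91 / 0.1856 = 193.5, so 194 as stated. Minimal detectable HR: exp(−2 × 1.96 / √194) = 0.755, against the stated 0.754.

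**Inputs from the documents.** Median PFS 11 and 16.9 months, 15% annual dropout, accrual over 43 months, primary cutoff at month 50 (Protocol 6.1); median OS 35 and 50 months (Protocol 6.4.2.1); final OS analysis at month 69 (SAP 4.7.1); 1:1 allocation.

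**Assumptions.** Exponential times. The PFS event is taken as progression. Mean post-progression survival of 26.5 and 35.7 months reproduces the OS medians. SREs are captured only to progression plus 1 month. The SRE hazard is equal in both arms, h = −ln(1 − p)/12 per month, where the 12-month risk p is 5% to 30%; for p = 20%, h = 0.0186. The documents give no SRE rate.

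**Rates used.** PFS hazards ln 2/11 = 0.0630 and ln 2/16.9 = 0.0410 per month; dropout −ln(0.85)/12 = 0.0135 per month.

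**Result.** Large-sample simulation, Cox HR (inavolisib/control), true HR 1, counts scaled to 160 per arm:

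| p | Cutoff (months) | Control recorded/true | Inavolisib recorded/true | HR, censored at survival contacts | HR, censored at last ascertainment |
|---|---|---|---|---|---|
| 5% | 50 | 7.6/12.2 | 9.2/13.2 | 1.15 | 1.00 |
| 5% | 69 | 8.7/15.7 | 11.2/17.6 | 1.19 | 1.02 |
| 10% | 50 | 15.0/23.7 | 17.9/25.5 | 1.14 | 1.00 |
| 10% | 69 | 17.0/30.0 | 21.7/33.7 | 1.20 | 0.99 |
| 20% | 50 | 29.2/44.8 | 34.6/47.8 | 1.14 | 1.00 |
| 20% | 69 | 32.5/54.9 | 40.4/60.7 | 1.18 | 1.00 |
| 30% | 50 | 42.6/63.3 | 49.8/67.4 | 1.14 | 1.00 |
| 30% | 69 | 46.7/75.3 | 57.0/82.6 | 1.18 | 1.00 |

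With SREs collected throughout, the HR is 1.00 to 1.01.

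**Events lost.** Control: from 1 − 42.6/63.3 = 33% to 1 − 8.7/15.7 = 45%. Inavolisib: from 1 − 49.8/67.4 = 26% to 1 − 11.2/17.6 = 36%.

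**Crude cross-check** (p = 20%, month 50). Capture is 34.6/47.8 = 0.72 on inavolisib and 29.2/44.8 = 0.65 on control. The ratio of the unrounded fractions is 1.11. The Cox value of 1.14 is a little higher, in part because patients with a missed SRE also stay in the risk set.

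**Trials of 320 patients** (4,000 per risk level, p 10% to 30%, month 50, survival-contact censoring). The HR exceeds 1 in 66% to 74%. A nominally significant result against inavolisib occurs in 6.0% to 8.5%, where 2.5% is expected.

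**Sensitivity** (p = 20%, month 50, survival-contact censoring unless stated):
- If 25%, 50% or 75% of later SREs are captured, the HR is 1.11, 1.05 or 1.03.
- If 12-month treatment stops without progression are 4.2% in both arms, it is 1.14; at 10% on inavolisib against 4.2%, 1.10; at 25% against 4.2%, 0.97. The 25% and 4.2% are the adverse event discontinuation figures that Protocol 1.2 quotes for the alpelisib trial, used here as 12-month probabilities.
- If the SRE hazard doubles or triples after progression, a true HR of 0.93 or 0.89 appears as 1.12 or 1.11. Censoring at last ascertainment gives 0.99 or 0.97.

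**The case against.** The text leans away from the harmful reading. The bullet just above in Protocol 6.4.3.1, on time to end of next-line treatment, censors at the last date known alive. Different words for SRE suggest that survival contacts were not meant. This carries weight but does not settle the date: survival contacts may be clinic visits, and Appendix 1 lists even a mid-cycle telephone call as a visit.

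A reader might infer that SREs are not collected at all. The documents do not support that. Appendix 1 is not an inventory of case report forms, and the eCRFs, including the long-term survival form named in Protocol 5.6, are not available. Protocol 5.3.5.9 also sends progression-type events to efficacy data and asks for uncertain ones to be reported as adverse events. What stands is that no collection is described; the efficacy data in that section read as RECIST tumor assessments, with no mention of SRE type or date.

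The size is modest. With 29 + 35 = 64 recorded SREs, the 95% interval spans a factor of exp(1.96 × 2/√64) = 1.63 either way, so a shift to 1.14 lies well inside it. The month-69 results matter only if SRE is updated at the final OS analysis, which neither document schedules. An on-study SRE endpoint with matching censoring would also be legitimate. The plan does not say that this is what it intends.

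**Conclusion.** The point holds as two gaps: no documented SRE collection, and a censoring date not tied to ascertainment. Under survival-contact censoring, a true HR of 1 would appear as about 1.14 to 1.15 at month 50 and 1.18 to 1.20 at month 69. This rests on the plan's PFS and OS medians, no capture beyond one month after progression, and assumed SRE rates. If censoring is at last ascertainment, the HR is about 1.00, but roughly a third or more of control-arm SREs go unrecorded, and analysis alone cannot recover them.

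A reader might conclude that the endpoint is biased against inavolisib. The documents do not support that as a fact. It depends on the reading of the censoring date, on how many later SREs are captured, and on why patients stop treatment: the direction reversed at 25% against 4.2% stops without progression. That is an outer case, since Protocol 1.3.2 reports that 4 of 157 patients (3%) stopped for an adverse event in the Phase I study of inavolisib.

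The conflict between Protocol 4.4.3 and 6.4.3.1 is plain from the text; its effect was not quantified. The endpoint is outside the testing sequence in SAP 4.3, so primary and key secondary conclusions are unaffected.

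**What to change.** 1. In Protocol 6.4.3.1 and SAP 4.4, censor patients without an SRE at the last visit or contact at which SRE status was recorded. This costs one sentence in each document.
2. Add an SRE item (yes/no, type, date) to Appendix 1 at existing visits and the 3-monthly survival contacts, recorded whether or not the event is attributed to progression. No new visits or imaging are needed. The cost is an amendment and an eCRF change across about 200 sites. Earlier post-progression SREs could then be found only by looking back. If the eCRF already holds such an item, citing it is enough.
3. If step 2 is not taken, state that the endpoint covers the on-study period only, name the data sources, and censor at the end of that period. This gives up later SREs but keeps the comparison fair.
4. Reconcile Protocol 4.4.3 with 6.4.3.1 on bone radiotherapy without progression, and carry the result into SAP 4.4, which has no counterpart to the 4.4.3 rule.

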6.4.3.2 Exploratory Patient Reported-Outcome Analyses

Summary statistics (mean, SD, median, 25th and 75th percentiles, and range) of linear transformed scores will be reported for the “worst pain” item of the BPI-SF, as well as all scales (symptoms, functional domains, and GHS/QoL) of the EORTC QLQ-C30 and BR23 questionnaire for each assessment timepoint. The mean change of the linear transformed scores from baseline (and 95% CI using the normal approximation) will also be reported independently for each treatment arm. Line charts depicting the mean and mean changes from the baseline assessment (and 95% CIs) of items and scales over time will be provided for each treatment arm. In the event of incomplete data, for all questionnaire scales, if more than 50% of the constituent items are completed, a prorated score will be computed consistent with the scoring manuals and validation papers. For scales with less than 50% of the items completed, the scale will be

considered as missing in accordance with the EORTC scoring manual guidelines (Fayers 2001).

Patient-reported outcome completion, compliance rates, and reasons for missing data will be summarized at each timepoint by treatment arm for each measure in ITT patients. The compliance rate will be based on the total number of patients expected to complete the questionnaire at a particular timepoint.

6.5 SAFETY ANALYSES

The safety analysis population consists of all patients who received at least one dose of study drug and is based on the treatment the patients actually received; that is, all patients who received at least one dose of inavolisib are included in the inavolisib plus palbociclib and fulvestrant group and all patients who received at least one dose of palbociclib and/or fulvestrant (and no inavolisib) are included in the palbociclib and fulvestrant group.

The safety objective for this study is to evaluate the safety of inavolisib plus palbociclib and fulvestrant compared with placebo plus palbociclib and fulvestrant on the basis of the following endpoints:

- Incidence and severity of adverse events, with severity determined according to NCI CTCAE v5.0
- Change from baseline in targeted vital signs
- Change from baseline in targeted clinical laboratory test results

The exploratory safety objective for this study is to evaluate tolerability of inavolisib plus palbociclib and fulvestrant compared with placebo plus palbociclib and fulvestrant from the patient's perspective, on the basis of the following endpoints:

- Presence, frequency of occurrence, severity, and/or degree of interference with daily function of selected symptomatic treatment toxicities as assessed through use of the NCI PRO-CTCAE and the “bother from side effects” item
- Change from baseline in symptomatic treatment toxicities, as assessed through use of the PRO-CTCAE and the “bother from side effects” item

Safety will be assessed through summaries of exposure to study treatment, adverse events, changes in laboratory test results, and changes in vital signs and ECGs.

Study treatment exposure (such as treatment duration, total dose received, and number of cycles and dose modifications) and dose intensity will be summarized with descriptive statistics.

All verbatim adverse event terms will be mapped to Medical Dictionary for Regulatory Activities (MedDRA) thesaurus terms, and adverse event severity will be graded according to NCI CTCAE v5.0. All adverse events, serious adverse events, adverse

events leading to death, adverse events of special interest, and adverse events leading to study treatment discontinuation that occur on or after the first dose of study treatment (i.e., treatment-emergent adverse events) will be summarized by mapped term, appropriate thesaurus level, and severity grade. For events of varying severity, the highest grade will be used in the summaries. Deaths and cause of death will be summarized.

Additionally, a shift table of selected laboratory tests will be used to summarize the baseline and maximum post-baseline severity grade. Changes in vital signs and ECGs will be summarized.

